Secondary Specific Aim #4. We will determine whether participants randomized to the high intensity exercise intervention have greater improvement or less decline in six-minute walk distance, physical activity, patient-perceived walking performance (measured by the WIQ distance and speed scores), and health-related quality of life measured by the SF-36 PF score at 26 week follow-up, compared to PAD participants randomized to the control group. We hypothesize that participants randomized to the high intensity exercise intervention will have greater improvement or less decline in each outcome at 26-week follow-up compared to the attention control group.

Secondary Specific Aim #5. We will determine whether participants randomized to the high intensity exercise intervention have greater improvement or less decline in six-minute walk distance, maximal treadmill walking time, physical activity, patient-perceived walking performance (measured by the WIQ distance score), and health-related quality of life measured by the SF-36 PF score at 52 week follow-up,

PROTOCOL TITLE: Low InTensity Exercise intervention in PAD: The LITE Trial

compared to PAD participants randomized to the control group. We hypothesize that participants randomized to the high intensity exercise intervention will have greater improvement or less decline in each outcome at 52-week follow-up, compared to the control group.

Secondary Specific Aim # 6.

Preliminary evidence suggests that ischemia-reperfusion, such as that experienced during high-intensity exercise in PAD, is associated with reduced muscle mitochondrial oxidative metabolism and increased oxidative stress (7-9). Therefore, in a randomly selected subset of participants, we will determine whether participants randomized to low intensity exercise (N=50) have greater improvement in calf muscle mitochondrial oxidative metabolism and lesser increases in calf muscle oxidative stress at 52-week follow-up, compared to the high-intensity intervention (N=50). We will also determine whether those randomized to low intensity exercise (N=50) and those randomized to high-intensity intervention (N=50), respectively, have greater improvement in calf muscle mitochondrial oxidative metabolism at 52-week follow-up, compared to the control group (N=50).

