F. High intensity, ischemic pain-inducing walking exercise may adversely affect calf skeletal muscle in people with PAD. Mitochondria are double membrane-enclosed organelles that generate adenosine triphosphate (ATP), the primary energy source for skeletal muscle cells (33). In patients with PAD, high-intensity exercise is associated with ischemia and subsequent reperfusion of calf skeletal muscle (7,38,39). Animal studies and preliminary human evidence show that re-perfusion of target tissue after ischemia increases oxidative stress, promotes mitochondrial dysfunction, and reduces ATP production (7-9,34-36). Preliminary human evidence suggests that high-intensity, ischemia-inducing walking exercise has harmful effects on calf skeletal muscle (36-39). We hypothesize that by avoiding the ischemia and re-perfusion associated with high intensity exercise, low-intensity exercise will promote more favorable calf muscle mitochondrial changes in PAD. We expect these favorable muscle changes will facilitate improved functional performance. Therefore, in our Secondary Aim #3, we will determine whether high-intensity, ischemic-pain inducing exercise increases calf muscle levels of oxidative stress and impairs calf muscle mitochondrial function, compared to low-intensity exercise. We will also determine whether low-intensity exercise improves mitochondrial function, compared to the control group. Because low intensity exercise is not associated with ischemia/reperfusion, we will not compare oxidative stress between the low intensity intervention and the control group.

G. Conceptual Model/Basis for our Study Design. Walking-related leg pain is a major deterrent to exercise in PAD (21-23). This phenomenon is not surprising from a behavioral perspective. According to Social Cognitive Theory (40,41), people's self-efficacy (confidence) in their ability to perform a health behavior and the behavior's incentive (reward) value are major determinants of adherence to healthy behaviors (42). Aversive physical symptoms (i.e. pain) that are associated with a behavior (i.e. walking) diminish the behavior's reward value, result in avoidance of the behavior,

[figure not shown]
PROTOCOL TITLE: Low InTensity Exercise intervention in PAD: The LITE Trial

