D. No prior studies have tested whether low-intensity exercise reduces calf muscle oxidative stress or increases calf muscle mitochondrial function compared to high intensity ischemia-inducing exercise. During high intensity exercise in people with PAD, metabolic demands for oxygen exceed oxygen supply. Calf muscle reperfusion occurs during rest, when blood supply becomes sufficient to meet calf muscle oxygen requirements. However, animal data and preliminary human evidence suggest that re-perfusion after ischemia increases oxidative stress and impairs mitochondrial function (7-9,35-39). We hypothesize that an exercise intervention that avoids ischemia will protect calf muscle against oxidative stress and improve mitochondrial function. This hypothesis has never been tested in people with PAD.

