S. Calf muscle biopsy measures. Muscle biopsies will be obtained on consecutive participants who provide informed consent for muscle biopsies until the required number of muscle biopsies is completed. Muscle biopsies may be obtained in up to 30 participants who are found to have a normal ABI consistent with the absence of PAD at their baseline visit. Muscle biopsies will be performed by co-investigator [name] MD, a neurologist with > 30 years of experience performing muscle biopsies. [name] completed all muscle biopsies for our pilot study (Section C3f). The biopsy will be performed in the medial head of the gastrocnemius muscle, at the point that is 67% of the distance between the medial malleolus and the medial aspect of the proximal tibia. This site represents greatest calf muscle diameter in >95% of individuals (88). Anesthesia is achieved with subcutaneous lidocaine. Subcutaneous and adipose tissue are dissected until muscle is identified. Approximately 250 mgs of muscle tissue is removed and immediately frozen at -70 degrees Celsius. The fascia is closed with absorbable suture. The wound is closed with subcuticular sutures and steri-strips. Participants return for a wound check one week later. At 52-week follow-up, we will repeat the measurement using identical techniques, at the site adjacent to the baseline incision. In the open biopsy, muscle tissue is directly visualized, ensuring an optimal muscle tissue sample and providing substantial advantages over the blind needle biopsy. If a participant refuses the open biopsy at either baseline or follow up, a Bergstrom needle biopsy will be offered, which involves using a Bergstrom needle to remove muscle. The Bergstrom needle biopsy method requires a small skin incision. Lidocaine is injected into the skin and subcutaneous tissue. A small incision of the diameter of the needle (5 mm) is made through the skin and superficial fascia of the muscle. The Bergstrom needle is a side-cut tool with a sharp end that includes an inner needle that obtains the muscle specimen. After the Bergstrom needle is advanced directly into the muscle, the inner needle is first withdrawn and then reinserted cutting the muscle that has pushed through the side cut of the outer needle. The entire apparatus is then removed and the specimen is examined. If that tissue is of insufficient size the technique can be repeated. The wound is closed with steri-strips. The biopsy will be performed at the same site as the planned open biopsy. This method avoids the long incision and need for sutures, but has the disadvantage of obtaining a smaller quantity of muscle tissue and has the disadvantage that the physician cannot directly see what tissue he/she is obtaining during the biopsy. Multiple passes with the Bergstrom needle will be required to obtain the amount of tissue usually obtained through the open technique. Specimens are shipped to the Univ. of Florida for measuring 3-nitrotyrosine with Western Blot (89) mitochondrial content (mtDNA copy number) measured by RT-PCR (90) and cytochrome c oxidase (COX) and citrate synthase activities using established methods (91-93). Muscle specimens may be sent to the Universities of Florida and University of Kentucky for analyses that include inflammatory biomarkers, markers of oxidative stress, measures of mitochondrial function and quantity, and muscle myofiber typing. Analyses may also be tested for protein measures of mitochondrial function, macrophages, satellite cells, and PCR/gene expression. Other measures related to skeletal muscle quality and function may also be performed.

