For our Primary Aim, we will use mixed model for repeated measures (MMRM) analysis to compare changes in six-minute walk performance at 52-week follow-up between the low vs. the high-intensity exercise group and between the low-intensity exercise group vs. the control group, respectively. To this end, the 26-week and 52-week changes of six-minute walk from baseline are treated as correlated outcomes, and independent variables include visit (26-week and 52 week), treatment (low-intensity, high-intensity, control), visit/treatment interactions and baseline six-minute walk performance. Unstructured variance-covariance matrix will be used to model the within-person correlations. In addition, we will also adjust for potentially imbalanced baseline confounders such as age, sex and baseline six-minute walk performance. When there is evidence that the normality assumption for the distribution of measures of interest is severely violated, we will perform Wilcoxon rank-sum test for the comparison. The nonparametric adjustment for the imbalance in mean difference of baseline covariates will be employed, when needed.

PROTOCOL TITLE: Low InTensity Exercise intervention in PAD: The LITE Trial

For Secondary Aim #1, we will use MMRM analysis to compare changes in six-minute walk, physical activity, and SF-36 PF and WIQ distance and speed scores at 26-week follow-up between the low- and high-intensity exercise groups and between the low-intensity exercise and control group, respectively.

For our Secondary Aim #2, we will use MMRM analysis to compare changes in maximal treadmill walking time, physical activity, and SF-36 PF and WIQ distance and speed scores at 52-week follow-up between the low- and high-intensity exercise groups and between the low-intensity exercise and control groups, respectively.

For our Secondary Aim #3, we will use normal approximation for binomial distribution to compare the proportion of participants who achieve adherence (as defined in section C18) between the low vs. high intensity exercise groups. We will also use logistic regression to compare the adherence rate between these two groups, adjusting for potentially imbalanced baseline confounders such as age, sex, and baseline six-minute walk performance. We will also use two sample two-tailed t-tests to compare adherence to the exercise intervention overall and at the prescribed intensity between the high vs. low intensity groups at 52-week follow-up.

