For our Secondary Aim #4, we will use MMRM analysis to compare changes in six-minute walk distance, physical activity, and SF-36 PF and WIQ distance and speed scores at 26-week follow-up between the high-intensity exercise and control groups.

For our Secondary Aim #5, we will use MMRM analysis to compare changes in six-minute walk distance, maximum treadmill walking time, physical activity, and SF-36 PF and WIQ distance and speed scores at 52 week follow up between high intensity exercise and control groups.

For our Secondary Aim #6, we will use two sample two-tailed t-tests to compare changes in COX, citrate synthase, and mitochondrial DNA at 52-week follow-up between the low intensity vs. the high-intensity exercise group and between the low-intensity exercise and control groups. We will also compare change in nitrotyrosine muscle measurements between the high-intensity exercise and the control groups. We will repeat these comparisons for the participants who adhere to their prescribed exercise intensity, measured by the ActiGraph.

For our Exploratory Aim #1, we will use two sample two-tailed test compare patients' perception to exercise at 52-week follow-up between high and low-intensity groups. For our Exploratory Aim #2, we will evaluate the effect of modified combo intervention (weight loss + LITE home-based exercise) on six-minute walk distance at approximately 12 week follow-up. This pilot study was completed in 2018.

The significance level for the Primary Aim will be 0.05/2 to adjust for two comparisons between low-intensity and high-intensity arms and between low-intensity and control arms.

The significance level will be 0.05 for all secondary aims. Furthermore, Secondary Aims #4 and #5 were pre-specified but added after the LITE Trial was underway in response to two negative trials of home-based exercise in patients with PAD demonstrating that a high-intensity walking exercise program did not improve six-minute walk or other outcomes in people with PAD (5, 6).

PROTOCOL TITLE: Low InTensity Exercise intervention in PAD: The LITE Trial

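### Secondary Aim #6 asks about oxidative stress in low versus high intensity exercise, but section 11.1 plans only a high-intensity versus control comparison of nitrotyrosine

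*Combined protocol and SAP*

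**What the plan says.** **The aim.** Section 1.2, Secondary Specific Aim #6, asks whether the low intensity arm shows "lesser increases in calf muscle oxidative stress at 52-week follow-up, compared to the high-intensity intervention". Where the aim turns to the control group, it names mitochondrial oxidative metabolism only.

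**The rationale.** Section 2.2 F gives the same contrast under an old aim number: "in our Secondary Aim #3, we will determine whether high-intensity, ischemic-pain inducing exercise increases calf muscle levels of oxidative stress", with low intensity as the comparator. Aim #3 is now adherence, as 11.1 shows: "For our Secondary Aim #3, we will use normal approximation for binomial distribution to compare the proportion of participants who achieve adherence". Section 2.2 F then excludes one contrast: "we will not compare oxidative stress between the low intensity intervention and the control group". Section 2.3 D lists as untested whether "low-intensity exercise reduces calf muscle oxidative stress or increases calf muscle mitochondrial function compared to high intensity ischemia-inducing exercise".

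**The measurement.** Section 9.2 S sends specimens "for measuring 3-nitrotyrosine with Western Blot" and says that others may be analysed for "inflammatory biomarkers, markers of oxidative stress, measures of mitochondrial function and quantity, and muscle myofiber typing".

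**The analysis.** For Aim #6, section 11.1 plans two-sample two-tailed t-tests on change in COX, citrate synthase and mitochondrial DNA, for low versus high and low versus control. It then adds: "We will also compare change in nitrotyrosine muscle measurements between the high-intensity exercise and the control groups". The comparisons are repeated in participants who kept to their assigned intensity. All secondary aims are tested at 0.05.

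**The power.** Section 11.2 gives 80% power for 0.61 SD with 50 participants per group, for all three pairs of arms. It names only citrate synthase, COX and mitochondrial DNA.

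**The concern.** The one analysis line on oxidative stress tests a contrast that the aim does not state, and the contrast that the aim does state has no line. Section 2.2 F has already ruled out low versus control, so the low intensity arm enters no listed oxidative-stress comparison, although the hypothesis is about that arm.

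Followed literally, 11.1 cannot answer the oxidative-stress part of Aim #6. If the investigators report high versus control as the Aim #6 result, they answer another question. If they report low versus high, the analysis plan has no line to support it. Timing matters as well: section 9.1 already describes a trial result, so a reader will want to know whether the contrast was fixed before the biopsy data were seen.

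The reach is limited to one secondary aim in a biopsy subset.

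**Working it through.** **1. Contrasts by source**

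| Source | Low vs high | Low vs control | High vs control |
|---|---|---|---|
| Oxidative stress: Aim #6 (1.2) | stated | not stated | not stated |
| Oxidative stress: 2.2 F | stated | ruled out | not stated |
| Oxidative stress: 11.1 | **absent** | absent | **listed** |
| Oxidative stress: 11.2 | absent | absent | absent |
| Mitochondrial markers: Aim #6 (1.2) | stated | stated | stated |
| Mitochondrial markers: 11.1 | listed | listed | absent |
| Mitochondrial markers: 11.2 | listed | listed | listed |

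The adherer analysis repeats the listed comparisons and adds no new contrast.

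**2. Which marker.** No section says that 3-nitrotyrosine is the Aim #6 oxidative-stress marker. I infer it, because it is the only non-mitochondrial muscle measure in the Aim #6 analysis. If another marker is meant, 11.1 has no line for that one either.

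**3. Reproducing the plan's figure.** Inputs from 11.2: 50 per group, 15% drop-out, two-sided alpha 0.05, 80% power. Completers: 50 × 0.85 = 42.5 per arm.

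- Detectable difference, normal: (1.960 + 0.842) × √(2/42.5) = 2.802 × 0.2169 = 0.608 SD. With the t distribution: 0.615 SD.
- Power at 0.61 SD: 0.803 (normal), 0.794 (t).

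The stated 0.61 SD is reproduced. The missing low-versus-high comparison uses arms of the same size, so its detectable difference in SD units is the same. This does not show that power is adequate for nitrotyrosine: 11.2 cites expected effects of 3.17, 2.12 and 0.75 SD for citrate synthase, COX and mitochondrial DNA, and none for this marker.

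**4. Can high versus control stand in for low versus high?** Two illustrations (t-test, 42.5 per arm):

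| True state | Low vs high | High vs control | Chance that high vs control is significant |
|---|---|---|---|
| Both exercise arms 0.61 SD above control | 0 | 0.61 SD | 0.794 |
| High equals control; low 0.61 SD below | 0.61 SD | 0 | 0.050 |

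The planned test can be positive when the answer to the aim is no, and null when it is yes. These are logical possibilities, not forecasts.

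**5. What one more test costs.** Section 11.1 lists 3 markers × 2 contrasts + 1 = 7 comparisons. Section 11.2 adds high versus control for 3 markers, giving 10. The fix makes 11. Chance of at least one false positive when no marker differs between arms (40,000 simulated trials, 42 per arm, three arms sharing data, four markers, simulation error about 0.002):

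| Assumed marker correlation | 10 tests | 11 tests |
|---|---|---|
| 0 | 0.356 | 0.385 |
| 0.3 | 0.341 | 0.365 |
| 0.5 | 0.308 | 0.329 |
| 0.8 | 0.239 | 0.250 |

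The documents give no marker correlation, so the range is an assumption.

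**The case against.** Four points can be made for the plan.

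- **The contrast is recoverable.** Protocol and SAP are one document. The aim fixes the contrast and time point; 11.1 fixes the Aim #6 test and level. This is fair, and it makes the repair easy. But 11.1 is not silent on the marker: it gives nitrotyrosine a sentence of its own with a different contrast, so an analyst has to choose between the two sections.
- **Low may behave like control.** Section 2.2 F argues that low intensity exercise does not involve ischemia and reperfusion. On that premise high versus control would track high versus low, and both illustrations above depart from it. This stands as a reason not to read 79% and 5% as estimates of harm. It does not replace the randomised comparison in the aim, because the premise is an assumption and the plan drops the one comparison (low versus control) that would test it.
- **It may be a drafting slip.** The group names in the two Aim #6 sentences could have been swapped. Nothing in the documents shows this, and the text would need correcting either way.
- **Section 2.3 D is a statement of novelty.** True. It supports intent only; the case rests on section 1.2, with 2.2 F in support.

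**Conclusion.** The concern holds. Sections 1.2 and 2.2 F set the oxidative-stress contrast as low versus high intensity. Section 11.1 lists nitrotyrosine for high versus control only, and 11.2 omits it. The count of planned low-versus-high oxidative-stress comparisons is 0 in 11.1 and 0 in 11.2.

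The mismatch itself is a matter of text and needs no assumption. Reading the nitrotyrosine sentence as the intended oxidative-stress test rests on the marker inference in step 2 of the working. The 79% and 5% figures rest on 0.61 SD and 15% drop-out, both taken from 11.2.

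This should be fixed, because a stated secondary hypothesis has no matching test and the sentence in its place answers another question. The primary analysis, its alpha and the sample size are not affected.

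**What to change.** **In 11.1, Secondary Aim #6:** add change in 3-nitrotyrosine (or whichever marker is meant) at 52 weeks, low versus high intensity, by the same two-sample two-tailed t-test at 0.05, as the oxidative-stress comparison for this aim. Keep high versus control and label it supportive.

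**In 1.2:** name the oxidative-stress marker in Aim #6.

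**Record:** date the edit, cite Secondary Aim #6 as its source, and state whether any biopsy results had been seen. If they had, present the edit as a clarification made after the data were seen.

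**In 11.2:** if the power statement is extended to this marker, say that no expected nitrotyrosine effect is available.

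**Minor:** list high versus control for COX, citrate synthase and mitochondrial DNA in 11.1, to agree with 1.2 and 11.2. Correct the old aim number in 2.2 F.

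**Cost:** wording only, since the planned biopsies and assays supply the data. There is one more unadjusted comparison (10 to 11), which raises the chance of at least one false positive by about 0.01 to 0.03 over the correlations tabulated. The adherer repeat also gains one comparison; it is well defined there because both exercise arms have a prescribed intensity.

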Exploratory Specific Aim 1. We will use qualitative methods to explore participants' perceptions of the exercise interventions in the high and low-intensity exercise groups, respectively, at 52-week follow-up.

Exploratory Specific Aim 2. In an exploratory specific aim, in up to 15 people with PAD and a body mass index $> 28 \text{ kg/M}^2$ who previously participated in the LITE Study or who were evaluated for participation, we will test the feasibility and efficacy of a 16-week weight loss intervention combined with the LITE home-based exercise intervention. The primary goals will be to determine whether it is feasible and effective to add a weight loss intervention to the LITE home-exercise intervention in people with PAD who are overweight. We will determine whether this modification of the LITE intervention (weight loss combined with the LITE home-based exercise intervention) can improve six-minute walk distance in people with PAD.

Exploratory Specific Aim 3. In an exploratory specific aim, in up to 30 people with PAD, we will determine whether, compared to placebo, nitrate-rich beetroot juice acutely improves six-minute walk distance or the short physical performance battery (SPPB), two-hours after nitrate-rich beetroot juice or placebo ingestion. We will also collect preliminary data to determine whether, as compared to placebo and as compared to nitrate-rich beetroot juice, far-red light (approximately 660 nm) alone and the combination of far-red light + nitrate-rich beetroot juice acutely increase plasma nitrite and improve six-minute walk distance, four meter walking velocity at usual or fast pace, or the SPPB, approximately two to three hours after far-red light treatment alone and the combination of far-red light treatment with nitrate-rich beetroot juice.

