
In addition, in a subset of participants we will obtain a muscle biopsy on the left and the right legs, respectively. These bilateral biopsies could be obtained at baseline, at 12-month follow-up, or both time points. The first biopsy will be performed as per our current procedures. The second biopsy will be performed seven days later when the participant returns for their incision site checks. It will be necessary for these individuals to remain off of their anti-platelet therapy for 14 days. Physician approval will be required. If the participant prefers to schedule the second biopsy at a later date (i.e. more than seven days after the initial biopsy), that will also be acceptable. In this case, anti-platelet

PROTOCOL TITLE: Low InTensity Exercise intervention in PAD: The LITE Trial

therapy will be held seven days prior to the contra-lateral biopsy. Participants will receive \$100 for their time and effort for each biopsy performed.

T. Qualitative measures. To achieve our Exploratory Aim, we will perform digitally recorded qualitative interviews among participants in the low and high exercise intensity interventions, respectively. We will assess participants overall perceptions of the exercise intervention and participant-identified facilitators and barriers to exercise behavior that is consistent with the study goals. Interviews will be performed under the direction of [name], a nationally-recognized expert in qualitative research. Prior work shows that theoretical saturation, or the point of redundancy at which no new themes emerge, often occurs in interview studies within the first 12 interviews; basic elements for themes may be present as early as six interviews (94). We will interview 15-20 randomly selected participants in each of the low- and high-intensity groups. Following transcription, responses to these open-ended items will be independently coded by the qualitative interviewers and [name] using content and constant comparative analysis (95-97).

U. Other measures. As in our previous trials, patient report will be used to document comorbidities. Patient report is highly correlated with comorbid disease measured with medical record review (98-101). Participants are asked to bring their medication bottles to each visit to assess medication use.

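### Exploratory Aim 1 is designed as a qualitative interview study, but the analysis plan assigns it an unnamed two-sample test with no defined variable and only 15-20 interviewees per arm.

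*Combined protocol and SAP*

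**What the plan says.** Section 1.2 sets the aim as qualitative: "We will use qualitative methods to explore participants' perceptions of the exercise interventions in the high and low-intensity exercise groups", at 52-week follow-up.

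Section 9.2.T gives a design to match. The interviews are recorded, and their content is open: "We will assess participants overall perceptions of the exercise intervention and participant-identified facilitators and barriers to exercise behavior". The size is stated as "We will interview 15-20 randomly selected participants in each of the low- and high-intensity groups", and the reason offered is that "theoretical saturation, or the point of redundancy at which no new themes emerge, often occurs in interview studies within the first 12 interviews". For the analysis, "responses to these open-ended items will be independently coded by the qualitative interviewers" together with one further named person, using content and constant comparative analysis.

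Section 8.1 labels the interviews exploratory. Table 4 in section 9.1 lists qualitative interviews at 52 weeks, for the two exercise arms only.

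Section 11.1 then gives the statistical analysis of the same aim: "we will use two sample two-tailed test compare" perceptions of exercise in the two arms at 52 weeks. It names no variable, no test statistic and no coding rule, and does not refer to the analysis in section 9.2.T. The same section sets significance levels for the primary aim and the secondary aims, and none for exploratory aims. The power section (11.2) does not cover this aim.

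**The concern.** The design and the stated analysis do not match. A two-sample test needs a variable measured on each participant. The interviews yield text, and the coding method is one in which themes emerge from reading it. If section 11.1 is followed as written, someone must decide after reading the transcripts which themes to turn into a variable, and how. The number of possible tests is then open, and nothing limits it.

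The sample was also chosen for another purpose. A number that suffices to stop hearing new themes is not a number that suffices to compare two arms.

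What is at stake is limited but real. Pain as a barrier to exercise is part of the trial's rationale (sections 2.2.D and 2.2.G), so readers will take an interest in how the two programmes were perceived. A significant result could reflect which theme was picked. A non-significant one could simply reflect 15-20 people per arm.

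**Working it through.** **Is there any variable for the test to use?**

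| Source | What it provides for this aim |
|---|---|
| Section 1.2 | qualitative exploration of perceptions |
| Section 9.2.T | open-ended responses, coded into themes; 15-20 per arm; saturation |
| Table 4 | interviews at 52 weeks, no score |
| WIQ and SF-36 PF (section 9.2.O) | perceived walking ability and physical functioning, not perceptions of the programme |
| Section 11.1 | a two-sample, two-tailed test of perception |

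Section 11.1 does not say outright that the test uses these interviews, but they are the only source defined for the aim. If another instrument was meant, it is undefined.

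**How large a difference could such a test detect?** The documents give no power figure for this aim, so there is none to reproduce. The method is first checked on the plan's own low- versus high-intensity contrast.

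*Inputs.* 120 per exercise arm less 15% drop-out = 102 (section 11.2). Interviewees: 15-20 per arm (section 9.2.T). Power 80%. Two-sided alpha 0.05 is an assumption for this aim, because none is stated.

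*Check of method.* The normal approximation to the detectable difference in SD units is (z for alpha + z for power) × √(2/n).
- Alpha 0.05: (1.960 + 0.842) × √(2/102) = 0.392. The exact t-test gives 0.394; the plan states 0.39.
- Alpha 0.025: (2.241 + 0.842) × √(2/102) = 0.432. The exact t-test gives 0.434; the plan states 0.43.

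*If a perception score existed.*
- n = 15: 2.802 × √(2/15) = 1.02; exact t-test 1.06 SD.
- n = 20: 2.802 × √(2/20) = 0.89; exact t-test 0.91 SD.
- Power for the 0.39 SD that the plan uses elsewhere for this contrast: 18% (n = 15) to 23% (n = 20).

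*If the frequency of a coded theme were tested.* Power = Φ[(|p1 − p2| − 1.96·SE0)/SE1], where SE0 = √(2·p̄(1 − p̄)/n), SE1 = √([p1(1 − p1) + p2(1 − p2)]/n), and p̄ is the mean of p1 and p2.

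Example with n = 15, p1 = 0.50, p2 = 0.942: p̄ = 0.721, SE0 = 0.164, SE1 = 0.143, and (0.442 − 0.321)/0.143 = 0.85, so power is 80%.

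Proportion needed in the second arm for 80% power:

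| First arm | n = 15 | n = 20 |
|---|---|---|
| 10% | 56.3% | 49.3% |
| 30% | 79.0% | 73.0% |
| 50% | 94.2% | 89.6% |

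Fisher's exact test, which suits these numbers better, is more demanding: from 10% it needs about 64% (n = 15) or 53% (n = 20).

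**The case against.** **A test is possible.** Content analysis can yield theme counts, interviewees are selected at random within arms, and section 11.1 says test, not t-test, so a comparison of proportions would fit the words. This stands. A reader might infer that the test cannot be run on such data, or that its p-value has no error rate at all. The documents do not support that. If one theme were fixed in advance and coded without regard to arm, Fisher's exact test at nominal 0.05 would hold its size: the true rate is at most about 0.025 at 15-20 per arm. What is missing is the fixed theme, the alpha and a rule for several themes.

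**Large contrasts may occur.** Section 9.2.A prescribes a pain level of at most 2 in one arm and 4-5 in the other. On a pain theme, 20% against 70% is conceivable, and Fisher's test would have 68% (n = 15) to 85% (n = 20) power for it. That is fair, but the documents give no expected frequencies, and smaller contrasts would usually be missed.

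**Coder bias.** A reader might infer that all coders did the interviews and know the arm. Section 9.2.T has one further independent coder, whose stated role is to direct the interviews, and says nothing on whether any coder knows the arm. The point should not rest on this.

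**The thematic analysis is already planned.** True, and section 11.1 does not cancel it. But it assigns this aim a test and does not mention the themes, so the two sections still need to be aligned.

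**Conclusion.** The point holds as a mismatch between a stated analysis and its own design, which goes beyond missing detail. As written, the test needs a variable built after the transcripts are read, without a stated alpha or multiplicity control. At the interview sample size it would detect only about 0.91-1.06 SD on a score, or theme frequencies such as 10% against about 50-57%, or 50% against about 90-94%. A positive result could come from the choice of theme and a negative one from the sample size, so neither could be interpreted.

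The figures assume two-sided alpha 0.05, 80% power, the normal approximation for proportions, and that the test is run on the 15-20 interviewees per arm.

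A reader might also infer that the trial's central claim, or its evidence on acceptability, depends on this test. It does not. The primary outcome is six-minute walk distance. Adherence is compared between the full exercise arms under Secondary Aim 3, with its own power statement. The issue is minor and confined to an exploratory aim.

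**What to change.** In section 11.1, replace the sentence on Exploratory Aim 1 with the analysis already described in section 9.2.T. State that themes will be reported by arm, descriptively, with no between-arm significance test. If theme counts are shown, give them with confidence intervals and label them hypothesis-generating. The intervals will make the imprecision plain: for a theme near 50% in both arms, the 95% half-width on the difference is about 1.96 × √(0.5/n), or 36 percentage points with 15 per arm and 31 with 20.

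Stripping arm labels from transcripts is not worth adding as a remedy for bias. Accounts of pain-inducing or comfortable walking would reveal the arm anyway.

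The cost is one sentence and the loss of a p-value for an exploratory aim. No sample size, primary analysis or secondary analysis changes.
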